#### TEST OF PERSONAL INSECT REPELLENTS

#### **SYNOPSIS**

The study pursuant to this insect repellent efficacy protocol is intended to provide data under the requirements of United Stated Environmental Protection Agency Guideline OPPTS 810.3700. This protocol, dated 8 September 2006, is a revision of EMD-004 as originally submitted to US/EPA on 27 April 2006. That protocol was dated 13 April 2006 (IRB approval date, 18 April 2006). Also on 27 April 2006, we submitted a related protocol, C-L-001, that provided certain information on subjects safety and recruitment. That information has been incorporated into the revision of EMD-004 presented here, and C-L-001 is no longer under consideration

This revision was made in response to the following principal sources:

- 1. June 27-30, 2006 EPA Human Studies Review Board Meeting Report (Proposed Final Draft v. 1 Dated August 28, 2006).
- 2. Product Performance Protocol Review by EPA staff [name], dated 6 June 2006.
- 3. Revised Draft OPPTS 810.3700. Product Performance of Skin-Applied Repellents of Insects and Other Arthropods dated 12 June 2006.
- 4. Science and Ethics Review of Protocol for Human Study of Mosquito Repellent Performance by EPA staff [name] and [name]. (review of draft revised protocol EMD-004, dated 12 July 2006), dated 28 August 2006.
- 5. Review pursuant to Title 3, California Code of Regulations Section 6710, Department of Pesticide Regulation, Worker Health and Safety Branch, and the Office of Environmental Health Hazard Assessment, dated 16 May 2006.

# 1 TITLE: TEST OF PERSONAL INSECT REPELLENTS

#### **2 PROTOCOL NUMBER:**

EMD-004

#### 3 SPONSOR:

EMD Chemicals, Inc.

# 4 PROTOCOL OBJECTIVE:

# **4.1** Type of Protocol:

This protocol will indicate the specific methods to be used and direct the conduct of the Study EMD–004. The study will be conducted in the laboratory at the letterhead address and at locales in nature with mosquitoes.

Note that this protocol formerly functioned in tandem with the general Carroll-Loye Protocol C-L-001, entitled "Protocol for Tests of Personal Insect Repellents". That protocol presented the domain of and universal instructions for conducting tests of this class, as formerly required by the California Environmental Protection Agency. Elements of Protocol C-L-001 have now been incorporated directly into this protocol, and C-L-001 no longer applies. Both that protocol and this protocol were developed by [name], Director of Research, Carroll-Loye Biological Research.

### 5 STUDY OBJECTIVE, RATIONALE AND STANDARDS:

### **5.1** Objective of Research:

To test the repellent characteristics of the Test Materials against mosquitoes, with efficacy measured as Complete Protection Time. Complete Protection Time, or CPT, is defined herein as the time between application of Test Material and the First Confirmed 'Lite with Intent to Bite.' A 'Lite with Intent to Bite', or 'LIBe', occurs when a mosquito alights on the treated test skin of a subject and extends its proboscis to the skin surface while ceasing locomotion. A 'First Confirmed LIBe' is that which is followed by another within 30 minutes. This work conducted pursuant to this protocol will be initiated by determining the amount of each of the repellents that subjects typically apply. Dosimetry will consist of a behavioral assay utilizing passive dosimetry.

# **5.2** Rationale and Main Endpoint:

This study will test the efficacy of new formulations of IR3535, created by the developer of IR3535, which are intended to increase cosmetic quality for better user acceptance. US/EPA requires new repellent formulations to be registered, and some registrants must present efficacy data as part of the registration review. The rationale for this study is to provide that efficacy data, which has not been previously collected. Compared to the insect repellent 'DEET' (N,N-diethyl-m-toluamide), there are few data examining the efficacy of IR3535 in different formulations. In addition, IR3535 has not been widely studied in the United States at end-product concentrations as high as those to be tested here. Yet the excellent

safety profile of IR3535 indicates that it is suitable for testing at higher concentrations than have typically been studied.

Stability of the end-products will be tested in a different study.

The main endpoint of this study will be the conclusion of a mosquito repellent efficacy study conducted in the field of three IR3535-based topical repellent formulations, with the data set suitable for submission to US EPA for insect repellent registration purposes. The efficacy study will consist of two field trials, with 10 treated subjects in each trial testing each formulation, and two untreated subjects in each trial. Initial dosage determination ('dosimetry') will be conducted with a set of 12 subjects, some of whom may then go on to participate in efficacy testing. Dosimetry will be conducted at the letterhead address. When 12 subjects have completed dosimetry, those data will be used to determine dosing for all efficacy trials with the actives, including those against other arthropods (i.e., including the tick repellent efficacy test, which is described in Carroll-Loye Protocol EMD-003). Protocol EMD-003, and this protocol, EMD-004, are independent in all other ways, except that individual subjects are not proscribed from participating in both studies.

# **5.3** Rationale for use of Human Subjects:

Human subjects are required because they represent the target system for the test materials, and sufficiently reliable models for repellency testing have not been developed. In addition, subjects will self-administer the test articles during dose determination. There are no accepted methods of modeling the complex relationship between spray delivery systems and target subjects. At least ten subjects are required in order to reduce variation around the population means we will describe. Data of this type are not available from other studies, and so it is advisable to test the comparatively large number of subjects proposed in case variance among them is high. The low toxicity of the test materials should mean that there is little incremental risk associated with increasing sample size. In addition, in pre-test meetings, human subjects were deemed appropriate by the same US/EPA toxicologist who also evaluated risk for the sponsor's Federal registration of the active ingredient.

#### **5.4** Balance of Risks and Benefits:

The study-associated risks are of three types: exposure to the test materials themselves, exposure to biting arthropods, and possible exposure to vectors of arthropod-borne diseases. As described below, subject health and safety are unlikely to be impacted by any study-associated risks during or after the study.

The repellent active ingredient has a low acute and chronic risk profile, established both through experimentation and through long-term consumer use. The concentrations of the active ingredient in the product being tested match those of products currently EPA-registered and marketed in the US. Subjects with known allergic reactions to insect repellents and common cosmetics are excluded from participating. 'Repeat' exposures during dosimetry are all of very brief before the repellent is washed off, and total a much briefer duration of exposure than a typical single consumer application likely would. Risks associated with inhalation and ingestion would require gross intentional mishandling by subjects, a scenario that the study methods do not promote.

The risk of a skin reaction to a mosquito bite is reduced by excluding candidate subjects who are aware of having a history of such reaction. In addition, subjects will be trained to quickly remove any mosquitoes that attempt to bite them, before penetration or injection of saliva if possible. Moreover, a stopping rule instructs subjects to cover any treated skin immediately if more than one mosquito attempts to bite during any exposure period. Subjects will be exposing small areas of treated skin for only 4 minutes per hour. Other parts of the body will be protected with provided netting. Subjects will be teamed with a partner for joint observation and experienced technical personnel will be present at all times to assist.

The US Centers for Disease Control estimates that about 1-in-5 people who become infected with West Nile virus will develop West Nile fever. Subjects are instructed to be alert for any flu-like symptoms (unusual tiredness or unusually severe headaches, body aches, fever, or a rash on the trunk of the body) for up to two weeks after the test. About 1-in-150 infected people will develop more serious symptoms, which will be described to the subjects. Most people (about 4 out of 5) who are infected with West Nile virus will not develop any type of illness.

In addition, the techniques employed to minimize exposure to mosquitoes and mosquito bites render the possibility of contracting a disease carried by mosquitoes very low. Field tests are being conducted in an area where such viruses have not been detected by county and state health or vector/mosquito control agencies for at least a month, so the risk is probably low that any individual mosquito present carries a disease. Only experienced professionals (the Study Director and/or other qualified researchers) will expose untreated limbs to monitor biting pressure, at the same infrequent, brief intervals as treated subjects, and with multiple assistants to remove any mosquitoes that lite with intent to bite.

In summary, the combination of technical precautions and natural factors means that the chances that any subject will contract West Nile fever or another disease from a mosquito bite are probably extremely small. There is probably no more risk to subjects than they would experience when engaged in normal outdoor activities in a similar rural area at the same time of year. If at anytime during the study a subject suffers a skin reaction or feels ill, he or she is instructed to inform the Study Director (i.e., the 'Principal Investigator'), or anyone else who is also working to direct the study). Such subjects will be immediately withdrawn from testing and medical management will be implemented (§9.5). Subjects may also request access to standard first aid materials (such as bandages, antiseptics, and mild topical and oral antihistamines) and request qualified first aid assistance at any time. Epi-Pens will also be on-site in case of Type 1 (anaphylactic) allergic reaction. At least one qualified researcher will remain with the other test subjects if other researchers depart with an injured or ill subject. Subjects are clearly and repeatedly informed that they may remove themselves for any reason from the study at anytime, without penalty to their compensation.

Against the slight risks are balanced substantial and reasonably likely benefits. Insect-borne disease is of growing significance in the United States and around the world where U.S. citizens are active. Discomfort associated with nuisance biting restricts many work and pleasure activities. DEET-based repellents have been the only reliable personal protection for many decades. However, health, comfort and practical concerns about DEET have restricted its use below a level ideal for public and personal health issues. The majority of marketed DEET-alternatives is of relatively very low efficacy. This study tests a repellent of well-known high efficacy, consumer safety and

acceptability. It is one of only two or three repellent actives that have ever been in a position to serve as a DEET-alternative of public health value. This study will give a good estimate of a minimum time of expected excellent protection, using standards, safety practices and design that are all conservative. Few studies have examined IR3535 at a concentration as high as that tested here. Hence its maximum potential efficacy, particularly as influenced by each specific formulation, is poorly known. Because EPA-registration requires efficacy data, a test such as this one is the only path toward further product development and greater availability of superior IR3535 products to consumers in the United States.

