# **6.1.7 Test Material Safety:**

EPA regulates use of inert ingredients (also termed "other" ingredients) by toxicology profiles in animal tests and by their inclusion in EPA lists of "approved" other ingredients. Ingredients on lists 4a or 4b are considered relatively safe for all uses. The ingredients in the proposed insect repellent formulations are mainly on lists 4a or 4b with a few ingredients on list 3 because of ocular irritation potential (e.g., alcohols). EPA normally regulates the presence of materials on list 3 by labeling to avoid contact with eyes and to prohibit application by children. The other ingredients in the test formulations are

commonly used in marketed products for application to human skin as components of cosmetic and drug formulations.

The insect repellent products proposed for registration have all been tested in animals for potential for oral and dermal toxicity, dermal inhalation, ocular and dermal sensitization potential; studies on droplet size of spray and aerosol products showed that there was little if any potential for inhalation exposure. These studies will be submitted and reviewed by EPA as part of the registration process. The results of these tests showed a low order of toxicity characteristic of similar tests on the "neat" active ingredient cited by EPA in approvals of this product for application on humans. The IR3535 active ingredient has an extensive, positive safety record of in consumer use.

MSDS documentation is the same as that submitted with the previous version of this protocol.

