#### 9.1.2 Exclusion criteria:

- 9.1.2.1 Known to be hypersensitive to mosquito bites or exhibiting hypersensitivity during test 9.1.2.2 Known to be sensitive or showing sensitivity to any of the test product ingredients after application. 9.1.2.3 Poor physical condition. 9.1.2.4 Unwilling to submit to brief query about personal condition. 9.1.2.5 Use of insect repellent within three days preceding the study. 9.1.2.6 Unwilling to refrain from use of perfumed products, alcoholic beverages or smoking after 9 PM the evening preceding the test and throughout the test. 9.1.2.7 Known to be pregnant or lactating. Pregnancy will be self-checked by each female volunteer on the morning of the repellent test using an OTC test kit provided by the Study Director. Results of each such test will be immediately verified by direct inspection by a female technician trained to make that assessment. Only volunteers scored as nonpregnant will be allowed to participate.
  - 9.1.2.8 Inability to deliver the test materials to own left and right limbs.
  - 9.1.2.9 Student or employee of the Study Director.
  - 9.1.2.10 Do not regularly spend time in outdoor settings.

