#### 9.1.4.2 Methods of Recruitment:

Our subjects are mainly University of California—Davis graduate and undergraduate students in life science programs with which the Principal Investigator is associated. Students in his laboratory who depend on him directly for employment or scholastically are not eligible to participate. Other subjects are science, education and health care professionals, and mosquito and vector control professionals.

We contact subjects who participated in previous Carroll-Loye repellent efficacy tests by selecting them from our Volunteer Database. At that time interested individuals often ask if one or more of their lab mates or acquaintances may participate as well. All such potential participants are screened or re-screened for suitability for each test in a private, one-on-one conversation held at the office of the Study Director. The Exclusion Criteria (section 9.1.2) are exercised by asking each candidate to address them in the interview with the Study Director. It is explained that pregnancy will be assessed directly in on the test day. The Study Director encourages candidates to ask questions and ask for clarification at any time during the interview and in all activities

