### 11.2 Replicates per Treatment:

For dosimetry, there will be 12 treated subjects, each serving as their own untreated control, testing each of the three repellent formulations. For repellency testing, there will be 10 subjects treated with each test repellent and two serving as untreated controls for repellency testing at each of two sites.

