# Insect Repellent Lotion with IR3535® (WV29-01)

Ingredient	INCI	(%)
PHASE A		
Water, demineralized	AQUA (WATER)	ad 100
1,3-Butanediol (Merck KGaA)	BUTYLENE GLYCOL	4.00
Titriplex® III (Merck KGaA)	DISODIUM EDTA	0.10
PHASE B1		
Rhodicare-S (Rhodia GmbH)	XANTHAN GUM	0.20
Carbopol ETD 2050 (Noveon)	CARBOMER	0.30
PHASE B2		
Triethanolamine (Merck KGaA)	TRIETHANOLAMINE	0.20
PHASE C		
Arlacel 165 VP (Uniquema)	GLYCERYL STEARATE, PEG-100	3.50
D 0i 2000 (400) (D	STEARATE	0.50
Dow Corning 200 (100cs) (Dow	DIMETHICONE	0.50
Corning)	IOODDODY/I DALAMTATE	4.00
Isopropyl palmitate (Cognis)	ISOPROPYL PALMITATE	4.00
Lanette 16 (Cognis)	CETYL ALCOHOL	1.00
Crodamol STS (Croda)	PPG-3 BENZYL ETHER MYRISTATE	2.00
IR3535 ®	ETHYL BUTYLACETYLAMINOPROPIONATE	10.00
Stearic acid (Merck KGaA)	STEARIC ACID	2.00
PHASE D		
Seibel 305 (Seppic)	LAURETH-7, POLYACRYLAMIDE, C13-14 ISOPARAFFIN	1.00
PHASE E		
Triethanolamine (Merck KGaA)	TRIETHANOLAMINE	0.10
PHASE F		
Paragon II/McIntyre	PROPYLENE GLYCOL, DMDM HYDANTOIN, METHYLPARABEN, PROPYLPARABEN	1.00

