# Appendix 2. Sample data recording forms.

C-L Field Record Mosq 8 hr

Test:	#	Note		Test	#	Note		Test :	=	Not	.	Test	=	Note	v-
	urtoes				urtoe				urtoes		r –		uitoes	14000	
Name				Nam			-	Name			-	Nam			
Time	appid:				appid:	:		Time	appid:		-		appld:		
	expose	ed:	-		expos				expose	d:	_	Time	expose	d:	
LIMB:		Left	Arm	LIMB:		Right	Arm	LIMB:		Left L	.ea	LIMB:		Right I	ea
	Bites*		Bites*				Bites*		Bites*		Bites*			Min	Bites*
5	211122	245		5		245		5		245		5	21002	245	
ΠŌ	-	250		10	-	250	-	10	-	250	-	10	-	250	_
15		255		15	-	255	-	15	-	255	-	15		255	
20		260		20		260	-	20		260	-	20	_	260	
25	-	265		25	-	265	-	25	_	265	-	25	_	265	
30		270		30	-	270		30		270		30		270	
35		275		35	-	275	-	35		275	-	35		275	
40	-	280		40	-	280	-	40		280	-	40		280	
45		285		45	-	285		45		285		45		285	
50		290		50		290	$\vdash$	50		290	$\vdash$	50		290	
55		295		55		295	$\vdash$	55		295	$\vdash$	55		295	
60		300		60		300		60		300	$\vdash$	60		300	
65		305		65	_	305		65		305		65		305	
70	$\vdash$	310		70	$\vdash$	310	$\vdash$	70		310	$\vdash$	70	-	310	
75	$\vdash$	315		75	-	315	$\vdash$	75	—	315	$\vdash \vdash$	75	<del></del>	315	—
80	$\vdash$	320		80	-	320	$\vdash$	80	$\vdash$	320	$\vdash$	80	-	320	—
85	$\vdash$	325		85	$\vdash$	325	$\vdash$	85		325	$\vdash$	85	-	325	
90	$\vdash$	330		90	$\vdash$	330	$\vdash$	90	_	330	$\vdash$	90		330	_
95	-	335		95	-	335	-	95	_	335	-	95		335	_
100	-	340		100	_	340	$\vdash$	100	_	340	$\vdash$	100	_	340	
	$\vdash$	345			-	345	$\vdash$		_	345	$\vdash$	105	_	345	
1105	-			105	-		$\vdash$	105	_		$\vdash$		_		
	_	350		110	_	350	$\vdash$	110	_	350	-	110	_	350	
115	$\vdash$	355		115	-	355	$\vdash$	115	_	355	$\vdash$	115		355	
120		360	_	120		360		120		360		120		360	
125	_	365		125	_	365	$\vdash$	125		365	$\vdash$	125		365	
130	$\vdash$	370	$\vdash$	130	$\vdash$	370	$\vdash$	130		370	$\vdash$	130		370	
135		3/5		135		3/5		135		3/5		135		3/5	
140	_	380		140	_	380	$\vdash$	140		380	$\vdash$	140		380	
145		385		145	$\vdash$	385	$\Box$	145		385	$\vdash$	145		385	
150		390		150		390		150		390		150		390	
155		395		155	$\vdash$	395	$\vdash$	155		395		155		395	
160		400		160		400		160		400		160		400	
165		405		165	$\vdash$	405		165		405	$\Box$	165		405	
170		410		170		410	$\vdash$	170		410	$\vdash$	170		410	
175	$\vdash$	415		175		415	$\vdash$	175		415	$\vdash$	175		415	
180		420		180		420		180		420		180		420	
185		425		185		425		185		425		185		425	
190		430		190		430		190		430		190		430	
195		435		195		435		195		435		195		435	

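### Section 5.4 claims an allergy exclusion that is broader than anything in the screening list in 9.1.2

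*Combined protocol and SAP*

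**What the plan says.** Section 5.4 offers the exclusion as one of its reasons for judging product risk low: "Subjects with known allergic reactions to insect repellents and common cosmetics are excluded from participating". This works at the level of product classes, so a candidate need not know which ingredient caused the reaction.

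The exclusion criteria in 9.1.2 contain ten items, two of which concern sensitivity. Item 9.1.2.1 covers mosquito bites. Item 9.1.2.2 covers the products: "Known to be sensitive or showing sensitivity to any of the test product ingredients after application". Section 9.1.4.2 makes this list the operative one: "The Exclusion Criteria (section 9.1.2) are exercised by asking each candidate to address them in the interview". The inclusion criteria in 9.1.1 say nothing about allergy.

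Section 6.1.7 describes the other ingredients as "commonly used in marketed products for application to human skin as components of cosmetic and drug formulations". Appendix 1 lists them, including for the lotion a preservative blend shown as "PROPYLENE GLYCOL, DMDM HYDANTOIN, METHYLPARABEN, PROPYLPARABEN".

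**The concern.** A safeguard cited in the risk-benefit argument should be one that screening puts into effect. Here the two sections differ in scope. To be caught by 9.1.2.2 before application, a candidate has to know that an ingredient of these products caused the past reaction. Someone who knows only that a lotion or repellent once gave them a rash meets the 5.4 description but not the 9.1.2.2 wording. Because the excipients are common cosmetic ingredients, such a history is relevant to these products.

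Section 5.4 also reassures the reader that "exposures during dosimetry are all of very brief before the repellent is washed off". That describes dosimetry only. In the field test the product is applied once and stays on the limb while protection time is measured. What is at stake is avoidable skin or allergic reactions in people the protocol says it will not enrol.

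**Working it through.** No published figure needs reproducing. The check is a comparison of texts, with some counts for context.

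**Step 1. Candidate histories against each section**

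| Candidate's history | Section 5.4 | Section 9.1.2, before application |
|---|---|---|
| Reacts to mosquito bites | Excluded | Excluded (9.1.2.1) |
| Reacted to a repellent or cosmetic and knows an ingredient of the test products was the cause | Excluded | Excluded (9.1.2.2) |
| (a) Reacted to a repellent or cosmetic, cause unknown | Excluded | Not excluded |
| (b) Reacted to a repellent or cosmetic, cause known and absent from the test products | Excluded | Not excluded |

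The remaining items, 9.1.2.3 to 9.1.2.10, cover physical condition, willingness to be queried, recent repellent use, perfume, alcohol and smoking, pregnancy or lactation, ability to self-apply, student or employee status, and time spent outdoors. None names an allergy. So 0 of 10 items exclude group (a) before exposure. The second limb of 9.1.2.2 removes such a person only once they react to the test product.

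The first row shows that the other exclusion claimed in 5.4, for bite reactions, does have a matching item.

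**Step 2. Ingredients a candidate might need to recognise** (Appendix 1, leaving out water and IR3535)

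- Lotion: 19 (triethanolamine appears twice and is counted once).
- Pump spray: 6, none of them in the lotion.
- Aerosol: 4, of which only isobutane is new.
- Distinct total: 19 + 6 + 1 = 26, or 25 if the two polyethylene glycol grades sharing a CAS number are counted once.

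**Step 3. Exposure where the product is not promptly washed off**

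Section 11.2 says "there will be 10 subjects treated with each test repellent" at each of two sites. With three formulations, 3 × 10 × 2 = 60 treated field slots. These are slots, not people in the gap.

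Wear time is not stated. As an assumption, it runs from the 180-minute mean used for planning in 9.1.3 (180/60 = 3 hours) to the end of the sample form headed "C-L Field Record Mosq 8 hr" (480/60 = 8 hours).

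**The case against.** The strongest reply is that only a mismatch of wording is shown, not that such candidates would enter the study.

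- **Consent form.** It is read aloud to each candidate before enrolment and may ask the broader question. It was not available here, so this possibility stands. It would reduce the practical risk but would not bring 5.4 and 9.1.2 into agreement.
- **Breadth of the interview.** It is private and one-on-one, 9.1.2.4 presupposes a query about personal condition, and the Study Director may refuse anyone. A candidate asked about ingredients might well volunteer an unexplained reaction. However, the query's content is not given and refusal is discretionary, so neither puts the stated exclusion into effect.
- **Low background risk.** Most subjects have taken part before, many have life-science training, and 6.1.7 reports animal testing, including for sensitization, with low toxicity. This supports a modest rating. It does not tell us how someone with an existing, unexplained cosmetic allergy would fare.
- **Care after a reaction.** Monitoring, washing, immediate withdrawal, antihistamines and Epi-Pens are specified. All act after exposure, and 9.5 itself allows for a rash appearing within 48 hours after the test day, which same-day stopping cannot prevent.
- **The counts do not size the gap.** Correct. In the main allocation a field subject receives one formulation, with 19, 6 or 4 excipients rather than 26. In dosimetry each subject uses all three. The figures give context only.
- **The word joining the two product classes in 5.4.** If it meant allergy to both repellents and cosmetics, group (a) would shrink, but the scope would still differ from 9.1.2.2.

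**Conclusion.** The concern holds. Section 5.4 relies on an exclusion at product-class level, while the list used for screening excludes only at test-ingredient level. Group (a) is the one that matters. For group (b) the documents show no added risk.

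The number of candidates affected cannot be derived from the documents. The conclusion rests on reading 9.1.2 as the operative list, which 9.1.4.2 supports, and leaves open what the consent form asks. It does not depend on the assumed wear time. This is a low-to-moderate safety correction that should be made. Sample size, protection-time estimation and dosimetry are unaffected.

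**What to change.** Add an item to 9.1.2 along the lines of: *Known allergic reaction to any insect repellent or common cosmetic.* Ask it explicitly in the 9.1.4.2 interview. Keep 9.1.2.2 as it stands, since it also covers sensitivity that appears after application. Wording the item with *or* settles the ambiguity in 5.4 on the protective side. Check that the consent form says the same.

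Narrowing 5.4 to match 9.1.2.2 would also make the text consistent, but by withdrawing a protection on which the risk-benefit argument relies.

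The cost is one line in the list and one interview question, plus the approvals that section 15 requires for changes bearing on subject safety. Some candidates will be screened out. Their number is unknown, and those in group (b) may have faced no added risk.
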